Three of these six units will be randomized (cluster randomized by units) in an intervention group and three in a comparison group. Each unit has about 40-60 nurses, approximately 260 nurses in total.

Data Collection

All nurses at all six units are asked to take part in the study by completing the PNKAS-N questionnaire at T-2 and T-3. Non-participant observational studies will be conducted at four units at T-2. Furthermore, one unit from the intervention group and one unit from the comparison group will be randomly chosen for observational studies at T-3. During each data collection period observations will be carried out for four-hour periods, two weeks per unit (40 hours per unit per occasions, 240 hours in total). Children older than six years who are having surgery at the time of data collection at the same two units will be asked to participate in an interview (20 children from two units) at T-2.

Data Analysis

Descriptive and inferential statistics will be used to analyse quantitative data at each data collection. Regression analyses that accounts for repeated measurements and cluster correlations (within units) will be used for comparisons between data collected at baseline T-1, T-2 and T-3. Content analysis will be used to analyse the children's responses to the interview questions. Supplementary data from the interviews and the observation studies at T-1 and T-2 will be compared to see if the tailored educational intervention improve nurses' pediatric pain management practice and childrens experience of pain assessment (e.g. use of pain assessment tools, use of pharmacological and non-pharmacological treatment of pain).

Ethics:

Ethical research guidelines will be followed (47-52). An approval from the Norwegian Social Science Data Services (NSD) and Regional Committee for Medical Research Ethics (REK South-East) will be obtained. Necessary approval from the hospitals will be obtained. Contact will be established with relevant persons at the units and cooperation on the implementation of the project. The project will be personally presented by the project manager at the relevant departments at baseline. A pilot observational study and two pilot interviews with children will be done before baseline (T-1).

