Participants (nurses, children and their parents) will receive oral and written information about the study, and informed consents will be obtained from all the participants. The information letter includes information about the study, and explains that it is voluntary to participate in the study and the participants' answers will be treated anonymously (53-57).

The questionnaires will be distributed to the nurses with an information letter and an envelope for returning the questionnaires. Informed consents will be obtained from all the persons (nurses, children and their parents) who are present during the observational studies. The participants who do not approve will be excluded from the study. Informed consents will be obtained from both the children (> 12 years) and the parents that are participating in the interviews. All data will be recorded on standardized forms. The interviews with children will be coded so that no data collected include date of birth or other sensitive information that can identify the child. Data will be stored securely and deleted at the end of the study (58-61).

Benefit/Risk:

Participating in the study will involve some extra work in filling in the questionnaire and to participate in the intervention. Furthermore, the participants may feel uncomfortable being observed during the observational study. They will be informed that no data about any nurses

or others will be available for others. It will also be voluntary to participate. Furthermore, the questionnaires are anonymous. Studying the nurses' knowledge and attitudes to pain in children and adolescents in Norway may lead to increased focus, awareness and attention on the topic among nurses. This means that while taking part in the study will not be of direct benefit to the children participating it may result in improved care for children in the future. The study will summarize Norwegian nurses' knowledge and attitudes to pain in children and adolescents. Further, the study will summarize nurses' use of pain assessment tools and if there are guidelines for pain assessment and treatment of the various units in the all health regions in Norway. The evaluation of the intervention can contribute to development of a national educational program for nurses in relation to post-operative pain and pain management in children and adolescents.

Declaration of Conflicting Interests:

There are no conflicts of interest.

Schedule 2014-2019

Preparation		November 2013 - June 2014	

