Date: 14.12.2017

Pediatric Pain Management Practices in Postoperative Units – an Intervention Study

Unique Protocol ID: 2014/7951

Secondary Ids: 2014/878 [Regional Committee for Medical Research Ethics Norway]

Statistical Analysis Plan

Changes in nurses' knowledge and attitudes of pediatric pain management

- Evaluated with "The Pediatric Nurses' Knowledge and Attitudes Survey Regarding Pain Questionnaire - Norwegian version" (PNKAS-N).

Data will be analysed using mixed models with repeated measures with the unit link as the dependent variable is considered continuous. Changes will be assessed as the overall change and changes at T1 (short term) and T2 (long term) adjusted for T0 (baseline). Baseline characteristics of the nurses will be entered as covariates and the study unit will be treated as a random factor. All analyses will be conducted using SPSS.

Nurses pediatric pain management practices in postoperative units

- Evaluated with non-participant observation using a structured observational tool (checklist) and field notes

The observational data will be analysed using NVivo (NVivo11) and Excel (Excel 2016), and frequency counts and proportions were calculated to summarize the data. A content analysis will be carried out on data within the field notes at T1, T2 and T3. Information in the field notes will be examined for common themes. Using NVivo (NVivo11), the researcher will code the data in each of the categories. After the data in the field notes are coded, the researcher will identify recurring themes and compare this to the data from the pain checklists to provide a picture of

current pain management practices. The data will be given to another experienced paediatric nurse who will code the data without any knowledge of the themes identified by the researcher, to minimize researcher bias. After having coded the data the researcher and the second coder will discuss and agree upon the final wording of the themes.

Children's experiences of pain and pain management after surgery

- Measured with Interview with children about postoperative pain using semi-structured interviews with children after surgery

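### The nurse questionnaires are called anonymous, but the planned repeated-measures model adjusted for baseline needs each nurse's forms joined; the documents must say which holds and name the matching model

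*Protocol*

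**What the plan says.** PNKAS-N is given to the nurses three times: before the intervention, and one and six months after it (Protocol, Study 1, Survey with Questionnaires). For the follow-ups, "All nurses at all six units are asked to take part in the study by completing the PNKAS-N questionnaire at T-2 and T-3" (Protocol, Study 3, Data Collection).

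On identification, Protocol, Benefit/Risk states: "Furthermore, the questionnaires are anonymous". Protocol, Ethics says of all participants that their "answers will be treated anonymously". It describes an information letter and a return envelope for the forms, with no study number or code. The only coding it mentions is for the children: "The interviews with children will be coded so that no data collected include date of birth".

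On analysis, Protocol, Study 3, Data Analysis plans regression that allows for repeated measurement as well as for correlation within units. The SAP, under nurses' knowledge and attitudes, says: "Data will be analysed using mixed models with repeated measures". It continues: "Changes will be assessed as the overall change and changes at T1 (short term) and T2 (long term) adjusted for T0 (baseline"). It then adds: "Baseline characteristics of the nurses will be entered as covariates and the study unit will be treated as a random factor". The SAP's T0, T1 and T2 for this outcome are the protocol's T-1, T-2 and T-3.

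**The concern.** A repeated-measures model at nurse level, with each follow-up score adjusted for the same nurse's baseline score, requires the forms to be joined by nurse. A form that is anonymous in the strict sense cannot be joined to another. The two statements conflict unless the word is used loosely.

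The answer decides which model is valid and what may be claimed. With linked forms, change within nurses can be reported and individual baseline scores used. With unlinked forms, the data are three cross-sections of the same units, the individual baseline term does not exist, and change within nurses cannot be reported. PNKAS-N is the only outcome for which the SAP gives an inferential model, so readers of the main effect paper need to know which case applies.

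**Working it through.** **1. The texts side by side.** There is no planned figure to reproduce, because the documents give no power, alpha, correlation or variance.

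- Without a link, each form is its own subject. With 6 units, 43 nurses and 3 waves, 6 × 43 × 3 = 774 forms would be 774 subjects with one row each. No within-nurse covariance can be estimated and no individual T0 score can be attached to a follow-up form.
- A model with arm, time, arm-by-time and random unit would still run if the unit is known for each form. Adjustment for T0 would then mean only a contrast with the baseline wave. Neither document describes this analysis.
- Nurse characteristics (age, education, experience, employment fraction) sit in an appendix of the form. They could serve as covariates without a link, taken from the same form.

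**2. A separate matter: the arm-by-time test when T0 is an outcome wave.**

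Inputs from the documents: 3 units per arm; 259 nurses, so m = 259/6 ≈ 43 per unit.

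Assumptions: total variance 1 at a wave; unit-by-time variance t = 1%, 2% or 5%; nurse-level variance s = 1 − t; correlation between one nurse's forms r = 0.5; the same nurses answering both waves; two-sided 5% test.

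- True SE of the arm contrast of change: √[(4/3)(t + s(1 − r)/m)]. At t = 0.01: √[(4/3)(0.01 + 0.99 × 0.5/43)] = 0.169.
- Reported SE, unlinked, unit the only random factor: √[(4/3)/43] = 0.176.
- Reported SE, linked, nurse and unit terms but no unit-by-time: √[(4/3)(s(1 − r) + t × 43 × 4/256)/43]. The 258 change scores leave 256 residual degrees of freedom, of which 4 carry the unit-by-time variance.
- False-positive rate: 2Φ(−1.96 ÷ (true/reported)).

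| | t = 1% | t = 2% | t = 5% |
|---|---|---|---|
| True SE | 0.169 | 0.205 | 0.285 |
| Unlinked, unit only: true/reported | 0.96 | 1.16 | 1.62 |
| False positives | 4.2% | 9.2% | 22.6% |
| Linked, nurse term, no unit-by-time: reported SE | 0.125 | 0.125 | 0.126 |
| True/reported | 1.36 | 1.64 | 2.27 |
| False positives | 15% | 23% | 39% |

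- Sensitivity of the unlinked ratios: 1.01, 1.20, 1.65 at r = 0.4; 0.85, 1.07, 1.56 at r = 0.7. If entirely different nurses answer, the term (1 − r) becomes 1 and the ratios are 1.19, 1.36, 1.76.
- Six unit mean changes compared on 4 degrees of freedom: the SE equals the true SE, and simulated false positives were 4.8% to 5.3%.
- What 4 degrees of freedom cost: the critical value is about 2.78, so significance needs an observed difference of 2.78 × 0.169 = 0.47 SD to 2.78 × 0.285 = 0.79 SD.

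**The case against.** The strongest reply is that "anonymous" is used loosely. It stands in a paragraph of reassurance to participants. The Ethics section applies similar wording to everyone, including children whose interviews are coded. The SAP, dated 14.12.2017, follows the last wave scheduled for September–October 2015, so its authors should have known whether forms could be joined when they specified baseline adjustment. The information letter could well describe a code. All of this stands, and it means the text does not show that the forms were unlinked.

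A reader might also infer that the SAP omits within-nurse correlation because unit is the only random factor it names. The wording does not support that. Repeated measures are specified in addition to the random unit, and the natural reading is that nurse correlation is modelled. What is missing is the name of the subject and the covariance structure.

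Finally, a reader might attribute the false-positive rates above to anonymity. They come from omitting an assumed unit-by-time variance, and linked forms without that term do worse than unlinked ones. With the same nurses answering, the true SE is the same with or without a code, so no loss of precision from anonymity as such is claimed for this contrast. If instead T0 is a covariate and both follow-ups are pooled, a random unit with small-sample degrees of freedom kept the arm test near 5% (simulated 4.3% to 5.4%).

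**Conclusion.** The conflict is real and unreconciled in the available text. If the questionnaires are literally anonymous, the nurse-level model with individual T0 adjustment cannot be run. It would be too strong to say that no analysis is possible, since a repeated cross-sectional model would run, or that this is the only inference planned, since the protocol also mentions unspecified inferential statistics at each wave.

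The linkage question has no numerical size of its own. Its consequence is which model is valid and whether within-nurse change may be reported. The error rates belong to the separate unit-by-time point, which applies whether or not forms are linked, but only if T0 is an outcome wave. They rest on assumed values of t and r: at 1% variance, unlinked forms from the same nurses give a test close to nominal, while at 5% either model is clearly anti-conservative. Confidence is medium, because the missing letter could resolve the linkage question. The point should be fixed before results are reported.

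**What to change.** Reconcile Protocol, Benefit/Risk and Ethics with Protocol, Study 3, Data Analysis and the SAP by stating whether the forms carried a code.

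- **If they did:** call them coded or pseudonymised, and name nurse within unit as the subject of the repeated measures, by a nurse random effect or a residual covariance, in addition to random unit.
- **If they did not:** replace the model by a repeated cross-sectional one with arm, time, arm-by-time, random unit and random unit-by-time, and a small-sample correction for six units. The six unit mean changes on 4 degrees of freedom are an alternative, equivalent only when unit sizes are balanced; the protocol gives about 40 to 60 nurses per unit. Take nurse characteristics from the same form, drop the individual T0 term and do not report within-nurse change.
- **In either case:** say whether T0 is a covariate or an outcome wave. If it is an outcome wave, include unit-by-time and small-sample degrees of freedom.

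The change is one sentence on linkage and a model statement, with no new participants or data. A code cannot be added now that the scheduled waves are past. The price is wider intervals for the arm-by-time test and, if unlinked, the loss of individual baseline adjustment.

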Date: 14.12.2017

Pediatric Pain Management Practices in Postoperative Units – an Intervention Study

Unique Protocol ID: 2014/7951

Secondary Ids: 2014/878 [Regional Committee for Medical Research Ethics Norway]

Statistical Analysis Plan

Changes in nurses' knowledge and attitudes of pediatric pain management

- Evaluated with "The Pediatric Nurses' Knowledge and Attitudes Survey Regarding Pain Questionnaire - Norwegian version" (PNKAS-N).

Data will be analysed using mixed models with repeated measures with the unit link as the dependent variable is considered continuous. Changes will be assessed as the overall change and changes at T1 (short term) and T2 (long term) adjusted for T0 (baseline). Baseline characteristics of the nurses will be entered as covariates and the study unit will be treated as a random factor. All analyses will be conducted using SPSS.

Nurses pediatric pain management practices in postoperative units

- Evaluated with non-participant observation using a structured observational tool (checklist) and field notes

The observational data will be analysed using NVivo (NVivo11) and Excel (Excel 2016), and frequency counts and proportions were calculated to summarize the data. A content analysis will be carried out on data within the field notes at T1, T2 and T3. Information in the field notes will be examined for common themes. Using NVivo (NVivo11), the researcher will code the data in each of the categories. After the data in the field notes are coded, the researcher will identify recurring themes and compare this to the data from the pain checklists to provide a picture of

current pain management practices. The data will be given to another experienced paediatric nurse who will code the data without any knowledge of the themes identified by the researcher, to minimize researcher bias. After having coded the data the researcher and the second coder will discuss and agree upon the final wording of the themes.

Children's experiences of pain and pain management after surgery

- Measured with Interview with children about postoperative pain using semi-structured interviews with children after surgery

Content analysis will be used to analyse the children's responses to the interview questions using NVivo (NVivo11) at T1 and T2. Children's responses to the interview questions will be transcribed verbatim by the researcher who conducted the interviews. Using NVivo (NVivo11), the researcher will code the data in each of the categories. After the data in the field notes are coded, the researcher will identify recurring themes and compare this to the data from the pain checklists to provide a picture of current pain management practices. The data will be given to another experienced paediatric nurse who will code the data without any knowledge of the themes identified by the researcher, to minimize researcher bias. After having coded the data the researcher and the second coder will discuss and agree upon the final wording of the themes.

Supplementary data from the interviews and the observation studies at T2 and T3 will be compared to see if the tailored educational intervention improve nurses' paediatric pain management practice and children's experience of pain assessment (e.g. use of pain assessment tools, use of pharmacological and non-pharmacological treatment of pain).

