Pain in children and adolescents is underestimated and undertreated even if a lot of research is done in the area (1, 2). Research suggests that lack of knowledge about pain and pain management in children are one of the reasons for the undertreatment (3-14).

As late as in the 1970's and 80's premature and newborn children went through surgery without pain medication (15) because it was claimed that the children could not feel pain since the nervous system was not fully developed. More recent studies show that preterm infants are hypersensitive to pain (16), and that surgery in the neonatal period can lead to prolonged pain and hypersensitivity in the damaged area (17, 18).

Untreated pain can cause unnecessary suffering, increased risk of complications, increased risk of morbidity and mortality, as well as lead to longer hospital stays and increased cost (19). Long-term consequences of inadequate relief of acute pain can be chronic pain for 10-50% of the patients, of which 2-10% of them will experience severe chronic pain (19).

Nurses who work at postoperative units have a considerable responsibility to ensure optimal pain management. Research shows that the use of guidelines and pain assessment tools improve the pain treatment of children through systematic assessment and evaluation (20, 11). However, more than half of European hospitals are reported to lack written guidelines for pain treatment and more than half of the patients experience severe pain (21, 22).

Pain assessment in children is largely based on patients' self-reports and nurses' assessment and the use of observational pain assessment tools (23, 24). There are many types of pain assessment tools for children (behavior form, face form, numerical scales) (11, 25-29), but no pain assessment tools are suitable for all children as it must be selected on the basis of the child's age, developmental level and context (27).

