During each data collection period, observations will be carried out for four-hour periods (day and evening), two weeks per unit (40 hours per unit per occasion, 240 hours in total). The observational study will focus on observing the nurses general pain management practice, pain assessment (use of pain assessment tools), use of pharmacological and non-pharmacological treatment of pain in children. A checklist and field notes will be used based on the PNKAS-N themes and essential areas of pediatric pain management identified in a literature review (36). Field notes will include descriptions of what is occurring during the period of observation and records of comments made by nurses related to pediatric pain management. The field notes will be recorded partly during the observation and partly after the observation (directly after), depending on the situation at the unit. No data about the child will be recorded except age, gender, type of surgery, and days since surgery. The other data that will be recorded is what the situation gives, but no data that can identify the patient will be recorded. The checklist will be pilot tested based on two different observation situations.

Data Analysis

Data from each nurse will be collected by using the pain management checklist and summarizing each of the nurses' pain management practices. A content analysis will be carried out on data within the field notes (37, 38). Information in the field notes will be examined for common themes (35, 39). Using highlighter pens, the researcher will code the data in each of the categories. After the data in the field notes are coded, the researcher will identify recurring themes and compare this to the data from the pain checklists to provide a picture of current pain management practices. The data will be given to another experienced pediatric nurse who will code the data without any knowledge of the themes identified by the researcher, to minimize researcher bias. After having coded the data the researcher and the second coder will discuss and agree upon the final wording of the themes.

c) Interview with Children

The aim of this part is to obtain more knowledge about what are the children's experiences of pain and pain management after surgery.

Sample

Twenty children older than six years going through surgery at the time of data collection at two of six units (randomly chosen), and their parents, will be asked to participate in this study.

Data Collection

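### The SAP judges observed practice from unadjusted counts and proportions with no between-arm contrast, so a change can reflect which units and children were watched

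*SAP*

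**What the plan says.** The protocol lists two research questions for Study 3. One concerns knowledge and attitudes, measured by the PNKAS-N questionnaire. The other asks whether the intervention improves practice, and the observation checklist is the quantitative measure of that.

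- **SAP, observation section.** For the checklist: "frequency counts and proportions were calculated to summarize the data". For the field notes: "A content analysis will be carried out on data within the field notes at T1, T2 and T3". The themes are then set beside the checklist data. The mixed model with nurse covariates and a random unit effect appears only under PNKAS-N.
- **SAP, closing paragraph.** "Supplementary data from the interviews and the observation studies at T2 and T3 will be compared", with the aim of seeing whether practice improved. No method is named.
- **Protocol, Study 3, Data Analysis.** "Descriptive and inferential statistics will be used to analyse quantitative data at each data collection". The next sentence promises regression that allows for repeated measurement and for correlation within units. Later in the same paragraph: "Supplementary data from the interviews and the observation studies at T-1 and T-2 will be compared", again without a method.
- **Protocol, Study 1 b), Data Collection.** "No data about the child will be recorded except age, gender, type of surgery, and days since surgery".
- **Protocol, Study 1 b), Data Analysis.** Checklist data are collected nurse by nurse, "summarizing each of the nurses' pain management practices".

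Observation covers six units at T-1 (Study 1 b), Sample), four at T-2, and one unit from each arm at T-3 (Study 3, Data Collection).

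**The concern.** The checklist results are meant to help decide whether the intervention changed behaviour at the bedside, yet the SAP states no contrast that could show this. It does not give the level at which a proportion is formed, the comparison between arms, any allowance for units, any measure of uncertainty, or any use of the child characteristics that the observer writes down.

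The two documents also name different waves for the comparison. On the labels in the SAP's observation section, which match the protocol's three waves, T2 and T3 both fall after the intervention, so that comparison contains no baseline.

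Two things change between waves whatever the nurses do. The set of observed units shrinks, and the children are different, because the waves lie months apart (protocol, Schedule). A crude rise or fall can come from either source. At stake is whether a reported improvement in practice, which the publication plan intends for the main effect paper, can be told apart from a change in who was watched.

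**Working it through.** **1. The plan's own figure.** Observation is 40 hours per unit per occasion.

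- T-1: 6 × 40 = 240 hours, as stated in Study 1 b).
- T-2: 4 × 40 = 160 hours. T-3: 2 × 40 = 80 hours. Together 240 hours, as stated in Study 3.

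The stated totals reproduce. Observed time falls 240, 160, 80 over the waves, so raw counts have no common base. Proportions do not share that fault, but they remain open to steps 2 and 3.

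**2. Change in the set of units.** The documents give no unit-level rates, so this is an assumed illustration: three units at 60% and three at 20% on some checklist item, equal numbers of episodes, and no unit changing over time. If episodes were combined over the observed units:

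- Six units: (3 × 60 + 3 × 20)/6 = 40%.
- Four units, of which one, two or three are high-rate: 30%, 40% or 50%, a change of −10 to +10 points.
- Two units, of which none, one or two are high-rate: 20%, 40% or 60%, a change of −20 to +20 points.

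Splitting by arm does not remove this, because each arm goes from three units at T-1 to one at T-3. Restricting the comparison to units seen at both waves does.

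**3. Change in the children.** Let a and b be the rates of a practice in two groups of children, and m the share in the first group. The crude proportion is m·a + (1 − m)·b. With a and b constant, the change between waves is (m₁ − m₀)(a − b).

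- Assumed a = 60%, b = 20%, m from 50% to 70%: the crude proportion goes from 40% to 48%, a rise of 0.20 × 40 = 8 points with no change in behaviour.
- Assumed range: a rate gap of 10 to 40 points and a mix shift of 10 to 30 points give 0.10 × 10 = 1 point to 0.30 × 40 = 12 points.
- Standardised to a fixed mix, the change is 0.

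These inputs are assumptions. They show that the mechanism is sound, not how large it is in this study.

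**4. What a comparison of arms would do.** If both arms had the 8-point shift in step 3, the difference of changes would be 8 − 8 = 0. If only one arm had it, 8 points would remain. Cancellation needs the same shift in both arms, effects that add, and an analysis that takes the difference of changes. The SAP does not specify that analysis.

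**5. How far inference can go.** With k of n observed units in the intervention arm, the smallest two-sided permutation p-value at unit level is 2/C(n,k).

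- 3 v 3: 2/20 = 0.10.
- 2 v 2: 2/6 = 0.33. This split at T-2 is assumed; the protocol gives four units without the division by arm.
- 1 v 1 at T-3: 2/2 = 1.0.

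So a unit-level analysis can give estimates with stated limits, but not a confirmatory test. At T-3 arm and unit cannot be separated by any model.

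**The case against.** The strongest reply is that the SAP departs little from the protocol. The observation part's own analysis section plans checklist summaries per nurse and content analysis, and the SAP largely repeats it. The regression sentence in Study 3 names no instrument, and both documents call the observation data supplementary when they turn to effect. The field-note analysis, with its second coder, is also more than a table of counts. Much of this stands, and it limits the weight of the point. But the protocol's sentence on inferential statistics covers quantitative data without exception, the checklist is quantitative, and themes from field notes do not estimate an effect.

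Four stronger readings are tempting and are not supported.

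- A reader might infer that the SAP pools all episodes, so that a nurse seen often dominates. The text does not say so; it leaves the level open, and the protocol's per-nurse summary is not withdrawn.
- A reader might infer that a promised case-mix adjustment was dropped. Neither document promised one; the unused child characteristics are a gap in both.
- The Background says of the pain assessment tool that "it must be selected on the basis of the child's age, developmental level and context". That concerns which tool suits a child. It does not show that the use of any tool varies with age.
- The 10 to 15 children operated on per day might suggest 100 to 150 child-days per unit over ten observation days (40 hours in four-hour periods, taken as one a day). That is unit throughput, not children observed, so it cannot show that fine strata are feasible.

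It is also fair that a case-mix shift common to both arms may cancel. That is a reason to specify the comparison of changes.

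**Conclusion.** The point holds in limited form. The SAP gives the checklist no between-arm contrast, no allowance for units, no statement of uncertainty and no use of the recorded child characteristics, yet compares the data to judge whether practice improved. The departure from the protocol is the missing inferential, cluster-aware analysis.

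The fall from 6 to 4 to 2 observed units follows directly from the documents and is the firmer threat to comparing waves. Case mix is a possible second source. Its size cannot be computed, because no observed rates or mixes are given; the 1 to 12 points rest wholly on the assumed gaps and shifts. A reader might conclude that any reported practice change is biased. The documents support only that it could not be distinguished from a change in who was observed.

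This should be changed. Because the data are supplementary, it does not touch the PNKAS-N analysis.

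**What to change.** Amend the SAP's observation section and closing paragraph as follows.

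1. For comparisons, replace raw counts with proportions over observed child episodes in which the practice applied, shown for each unit at each wave, grouped by arm.
2. Compare the change from T-1 between arms, using only units observed at both waves, and reconcile the waves named in the SAP with those in the protocol.
3. As a supporting analysis, adjust at episode level for coarse age band and surgery group, by regression or standardisation, with clustering by nurse and unit recognised, and only then summarise by unit. The order matters: averaging within nurse or unit first removes the strata needed for adjustment.
4. Label the results descriptive and give intervals only where the number of units allows. State that at T-3, with one unit per arm, arm and unit are confounded and no unit-level interval for the arm contrast is available.

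The cost is SAP wording and some more tabulation on data the protocol already planned to record. Cells will be sparse, so strata must be coarse. The checklist is not in the documents; if it does not record when a practice applied, or does not link episodes to the child's characteristics, the SAP should say so and stop at step 2 with the denominator that is available. The SAP is dated December 2017 and the protocol scheduled the last wave for September to October 2015, so the change should be recorded as made after planned data collection.
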